#### DATA SHARING AND OWNERSHIP

During the conduct of the trial, the study database will remain confidential. After study completion, access to data will follow requirements of the Infectious Diseases Institute, National Institutes of Health and the University of Washington. The University of Washington International Clinical Research Center has a Manuscripts and Ancillary Studies Committee established to enable data and specimen collaborative work from studies conducted through the research group. Intellectual property and data generated under the proposed project will be administered in accordance with Uganda, University of Washington and NIH policies, including the National Guidelines for Research involving Humans as Research Participants (2014) and the NIH Data Sharing Policy and Implementation Guidance of March 5, 2003.

Materials generated under the project will be disseminated in accordance with University/participating institutional and NIH policies. Depending on such policies, materials may be transferred to others under the terms of a material transfer agreement. Access to databases generated under the project will be available for educational, research and non-profit purposes as approved by the relevant IRBs. Publication of data shall occur during the project, if appropriate, or at the end of the project, consistent with normal scientific practices. We will publish our findings in a timely fashion and will present unpublished data at appropriate research conferences. We are committed to collaboration in complex disease research and will participate in data-pooling studies as allowed by our currently established consent forms and IRBs.

Data obtained from this research study are the property of the Infectious Diseases Institute of Makerere University and the University of Washington International Clinical Research Center.

Local researchers shall have unrestricted access rights to datasets collected through this collaborative research project in accordance with Uganda guidelines.

#### DISSEMINATION PLAN

Dissemination of study results will follow principles of good participatory practice. Study results will be disseminated through presentations to study participants, stakeholders and policy makers, and published in conference abstracts and peer-reviewed journals. Participants will be informed that if they so desire, they will be contacted at the end of the study for the purpose of informing them about study results. Trial results will also be shared with the community advisory board, the Ministry of Health, implementing partners and civil society groups with interest in reproductive health.

#### HUMAN SUBJECTS CONSIDERATIONS

The study protocol, site-specific informed consent forms, participant education and recruitment materials, and other requested documents — and any subsequent modifications — will be reviewed and approved by the IRBs/ECs responsible for oversight of research conducted at the study site. Subsequent to initial review and approval, the responsible IRBs/ECs will review the study at least annually.

#### Informed consent

Written informed consent will be obtained from each study participant prior to both screening and enrollment. Participants will be offered copies of the informed consent forms. The study site will draft informed consent forms that describe the purpose of screening and of the study, the procedures to be followed, and the risks and benefits of participation, in accordance with all applicable regulations, based on the consent forms provided in the Appendix. The site will translate the forms into the local language and verify the accuracy of the translation by performing an independent back-translation, which will be reviewed and approved by the International Clinical Research Center at the University of Washington.

#### Risks

*Confidentiality*. Although the study site will make every effort to protect participant privacy and confidentiality, it is possible that participants' involvement in the study could become known to others, and that social harms may result (i.e., because participants could become known as participating in a trial involving HIV-positive persons). For example, participants could be treated unfairly or discriminated against, or could have problems being accepted by their families and/or communities. There is additionally the potential of confidentiality with regards to virtual data collection over the phone. Phone visits may occur, to comply with national safety guidelines in response to COVID-19. Study staff are well trained in protecting patient confidentiality, and will ask several introductory questions to confirm the identity of the participant before continuing with study visits. Phone visits will only occur if participants feel comfortable answering study questions virtually, and they do not foresee any safety related concerns.

*HIV testing*. Participants may become embarrassed, worried, or anxious when completing their HIV risk assessment and/or receiving HIV counseling. They also may become worried or anxious while waiting for their (or their partner's) HIV test results. Couples-based counseling and

discussions of study participation may raise issues between partners, particularly related to blame (from HIV-negative men) and potential termination of the partnership. Participants who learn that they have HIV may experience anxiety or depression related to their test results. Individual and couples-based HIV counseling will be provided by counselors and clinicians who have been trained in specific issues related to HIV serodiscordant couples, including stigma, blame, methods to avoid transmission, and available support services.

Social harm. Intimate Partner Violence (IPV) following HIV status disclosure is an important consideration for couple studies. In a Kenyan study, women who experienced recent IPV were less likely to report partner self-testing (adjusted relative risk ratio [a RRR] 0.10; 95% CI: 0.02-0.47) or couple testing (a RRR 0.13; 95% CI: 0.03-0.54)[86]. Recent partner violence was not significantly associated with male partner self-testing or couple testing. However, couple testing was less likely if the male partner had a neutral or negative reaction to the offer of a self-test (aOR 0.32; 95% CI: 0.12-0.87) or was not easily persuaded to use a self-test (a OR 0.25; 95% CI: 0.09-0.76).

We have extensive experience with counseling >1700 couples over the past decade at the IDI-Kasangati research site. In a study that utilized data from our site, IPV was reported in 2.7% of visits by HIV-infected women and in 2.2% of visits by HIV-uninfected women [87]. In the Partners PrEP Study, HIV-uninfected women in serodiscordant partnerships reported IPV at 0.7% of study visits [88]. Serodiscordant couples perceive PrEP as a solution to the "discordance dilemma" the desire to avoid HIV acquisition while preserving the relationship. PrEP users benefit from the adherence support of infected partners on ART, and this mutual reinforcement motivates couples who wish to stay together to do so [52].

The majority of women receive support and understanding from their partners when they disclose their HIV status. Fewer than 5% of couples separate or divorce after disclosure of an HIV positive test [89]. A study in South Africa found no evidence that inviting male partners to ANC and HTS increased risk of self-reported IPV in women or men when compared to letters inviting male partners for pregnancy information sessions [36]. Overall, no association between HIV status and IPV was demonstrated in an analysis of data from Demographic and Health Surveys conducted in Kenya, Liberia, Malawi, Mali, Rwanda, Zambia and Zimbabwe [90].

While HIVST studies indicate several benefits and minimal risk of harm, intended or unintended physical, economic, emotional or psychosocial injury could occur before, during or after HIV testing [91]. Women may experience social harm from partners after discussing and/or performing HIVST. In a Kenyan cohort study, two of 178 pregnant or postpartum women reported verbal abuse following a reactive HIV self-test result [46]. Few instances of violence or harm have been reported in HIVST randomized trials, but these occurred prior to partner notification[92-94], suggesting that HIVST may not directly influence the risk of IPV. This finding is consistent with systematic reviews of harm in studies of HIVST [95], couple testing [96], and other forms of HIV testing [97].

*Phlebotomy*. Participants may experience discomfort or pain when undergoing phlebotomy. They also may feel dizzy or faint, and/or develop a bruise, swelling, or infection where the needle is inserted.

*PrEP medication.* Risks and side effects related to PrEP include: occurring in a minority of individuals taking PrEP - gastrointestinal intolerance, such as nausea, diarrhea or vomiting, flatulence; rare but serious - lactic acidosis/ severe hepatomegaly with steatosis, renal impairment, including cases of acute renal failure and Fanconi's syndrome (renal tubular injury

with severe hypophosphatemia), increase in bone metabolism leading to osteopenia, hypersensitivity reaction.

*Qualitative interviews.* The risks of participating in the qualitative interviews are minimal. It is possible that participants might become tired during the interview. They may also find some of the questions uncomfortable or hard to answer. In the observation sessions, it is possible that individuals may feel uncomfortable being observed.

#### Benefits

The primary aim of this study is to evaluate the impact of innovative strategies on male partner HIV testing, engagement in HIV care and prevention among men, and on post-partum ART continuation and adherence among HIV-positive women. HIV prevention practices, according to Ugandan guidelines, will be provided to all participants enrolled in this study. This will include risk reduction counseling, treatment of sexually transmitted infections (STIs), condoms, and referral for medical male circumcision. If prevention strategies are modified during the course of study conduct (e.g. PrEP becomes available through the public health system), participants will be counseled and referred for these strategies as well.

HIV-positive women will benefit from male partner testing, facilitated disclosure and ART counseling. HIV-negative male partner participants will benefit by having free access to PrEP during the study period, until 6 months after their partner initiates ART. Participants may benefit from ongoing access to prevention services. There may be no other direct benefits to participants in this study. However, participants and others also may benefit in the future from information learned from this study.

All participants will be provided with HIV prevention services, including condoms, STI treatment, and ongoing support, including counseling and referral to other support services.

#### Care for HIV-positive male partners

This study will identify male partners who are infected with HIV, either as part of testing male partners of unknown status, or during follow-up of initially HIV-negative men. Study staff will provide participants with their HIV test results in the context of post-test counseling. Men identified as HIV-positive will be referred for HIV clinical care, including primary care and antiretroviral therapy, according to Ugandan guidelines. During the course of the study, it is possible that guidelines will change regarding clinical care of persons with HIV (including optimal therapy, prophylaxis, etc.). At all times during the study, treatment and referral practices for HIV-positive participants will be provided referrals to other care programs for ongoing HIV primary care. This type of care will also be offered to initially HIV-negative study participants who become infected during follow-up.

#### Benefits to the community

An important goal of this study is to achieve the study objectives in a way that provides benefits to the community that endure beyond the proposed study lifetime regardless of the specific outcome of the study. Some of these community benefits are listed below:

Couples HIV counseling and testing (CHCT): Infrastructure to effectively counsel and test couples for HIV will be needed for this study to effectively recruit male partners. CHCT capacity developed

at the study site in collaboration with existing local VCT programs through training of local counselors is a beneficial resource to the community well after the study is completed. Given recent data that 70% of incident HIV cases are transmitted from regular partners, creating awareness, increasing demand, providing couples VCT and providing ART and PrEP will reduce transmission of HIV among couples. This will have consequent benefits to the family and community by maintaining one healthy partner.

Development of male-friendly HIV testing and linkage to HIV care and prevention within real world PMTCT B+ settings: This study aims to provide HIV prevention policy makers with information on how to best engage male partners in PMTCT B+ programs. In addition to the provision of this biomedical method, the study site will provide CHCT, and routine adherence counseling. The outcome of the study will be evidence upon which to based policy guidelines for improving male involvement in PMTCT in Uganda and nearby countries with similar HIV prevention needs.

#### Treatment for injury

If a study participant is injured while participating in this study, they will be offered care at the study clinic, free of charge until their injury is cured or stabilizes. Participants will be encouraged to tell members of the team of researchers if they feel they have been injured because of taking part in this study. Those who require medical care that the study clinic cannot provide will be referred by the study doctors to the appropriate services or organizations that can provide care for the injury. This referral will be covered by the University of Washington comprehensive liability program.

#### Study records

Site Investigators will maintain, and store in a secure manner, complete, accurate, and current study records throughout the study. The investigator will retain all study records for at least five years after completion of the study. Study records include administrative documentation and regulatory documentation as well as documentation related to each participant screened and/or enrolled in the study, including informed consent forms, locator forms, case report forms, notations of all contacts with the participant, and all other source documents. Logs linking participant name to study identification number and other identifying information in study files will be retained for five years after the study is completed; after that time, the link will be destroyed. Participants may consent to storage of samples for future research; any future research must be approved by overseeing Institutional Review Boards.

#### **Confidentiality**

Every effort will be made to protect participant privacy and confidentiality to the extent possible. Personal identifying information will be retained at the study site. The study site will establish a standard operating procedure for confidentiality protection that reflects the local study implementation plan and the input of study staff and community representatives to identify potential confidentiality issues and strategies to address them. In addition to local considerations, the protections described below will be implemented at the study site.

All study-related information will be stored securely at the study site. All participant information will be stored in areas with limited access. Data collection, administrative forms, laboratory

specimens, and other reports will be identified only by a coded number to maintain participant confidentiality. All records that contain names or other personal identifiers, such as locator forms and informed consent forms, will be stored separately from study records identified by code number. All local databases will be secured with password-protected access systems. Forms, lists, logbooks, appointment books, and any other listings that link participant ID numbers to other identifying information will be stored in a separate, locked file in an area with limited access.

Participants' study information will not be released without their written permission, except as necessary for oversight by:

The National HIV/AIDS Research Committee The Uganda National Council for Science and Technology The Uganda National Drug Authority Uganda Ministry of Health The University of Washington Harvard Medical School The United States National Institutes of Health

	ANTENATAL				PC	OSTN	ΑΤΑ	L
	T1	T1 T2		T4	M3	M6	M9	M12
ADMINISTRATIVE AND REGULATORY PROCEDURES								
Obtain written informed consent	[X]	[X]	[X]	[X]				
Assign participant identification number	[X]	[X]	[X]	[X]				
Assess eligibility	[X]	[X]	[X]	[X]				
Collect/update locator information	[X]	[X]	[X]	[X]	Х	Х	Х	Х
Collect/update demographic information	[X]	[X]	[X]	[X]				
Obtain random allocation	[X]	[X]	[X]	[X]				
Schedule next visit	[X]	[X]	[X]	[X]	Х	Х	Х	
COUNSELING								
HIV/STI risk reduction counseling, condom provision	[X]	[X]	[X]	[X]	Х	Х	Х	Х
Counseling (ART adherence, clinical & prevention benefits)	[X]	[X]	[X]	[X]	х	х	Х	Х
CLINICAL PROCEDURES								
Provide HIV test results	[X]	[X]	[X]	[X]				
Medical history	[X]	[X]	[X]	[X]	Х	Х	Х	Х
Perform physical exam	[X]	[X]	[X]	[X]	[X]	[X]	[X]	[X]
STI syndromic assessment and management	[X]	[X]	[X]	[X]	[X]	[X]	[X]	[X]
Referral for / provision of ART according to national guidelines	[X]	[X]	[X]	[X]	х	х	Х	х
PMTCT PROCEDURES*								
Antenatal care package	[X]	[X]	[X]	[X]				
Postnatal care package					[X]	[X]	[X]	[X]
Infant HIV status at 6 weeks					Х			
Infant survival at 12 months post-partum								Х
LABORATORY PROCEDURES								
Syphilis testing	Х	[X]	[X]	[X]				
HIV serology	Х	[X]	[X]	[X]				
Plasma HIV viral load						Х		Х

#### Table 5. Procedures for HIV-positive pregnant women

\*Standard of care

Study staff will perform study specific procedures at collaborating clinics

#### LEGEND

[] as indicated T = trimester Del = delivery

	Ε	M3*	M6	M9	M12	[M]⁺
ADMINISTRATIVE AND REGULATORY PROCEDURES						
Obtain written informed consent						
CLINIC PROCEDURES						
Confirmatory testing (self-test arm)	Х					
Initial testing (invitation letter arm)	Х					
Provide HIVtest results and post-test counseling	Х					
Medical history	Х	Х	Х	Х	Х	
Perform physical exam	Х	[X]	[X]	[X]	[X]	[X]
STI syndromic assessment and management	Х	[X]	[X]	[X]	[X]	[X]
Syphilis testing	Х					
HIV-NEGATIVE MEN						
Provide HIV test results		Х	Х	Х	Х	[X]
Hepatitis B surface antigen						
Creatinine			Х		[X]	[X]
PrEPprovision	Х	Х	Х	[X]	[X]	[X]
Blood sample archive for tenofovir levels (if on PrEP)		Х	Х			
HIV-POSITIVE MEN						
Referral for / provision of ART according to national						
guidelines	Х	Х	Х	Х	Х	[X]
Assess ART use and linkage/retention in care		Х	Х	Х	Х	[X]
Plasma HIV viral load	Х		Х		[X]	[X]

Table 6. Procedures for male partners

[] as indicated \*Three months after study enrollment \*Visits up to 12 months postpartum

	Possible seroconversion visit (≥1 rapid HIV test positive)	Follow-up to possible seroconversio n (ideally within one month of possible seroconversio n)	M3	M6
ADMINISTRATIVE, BEHAVIORAL AND REGULATORY PROCEDURES				
Provide HIV counseling, including couples counseling	Х	Х	Х	Х
CLINICAL PROCEDURES				
Collect medical history	Х	Х		Х
Perform physical exam	Х		Х	Х
Collect blood specimen	Х	Х	Х	Х
Stop PrEP, if applicable	Х			
Provide test results	Х	Х		
Refer for HIV care		Х		
Assess linkage to care			Х	Х
LABORATORY PROCEDURES				
CD4 count	Х	Х	Х	Х
HIV plasma viral load	Х	Х	Х	Х
HIV serology (confirmatory EIA)	Х			
Serum, plasma archive for HIV resistance assays, PrEP levels (batched testing)	Х	х	х	х

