#### STUDY METHODS

#### Overall design

This is a randomized trial of HIV-positive pregnant women and their partners. The overall goal is to evaluate the impact of innovative strategies on male partner HIV testing, and engagement in HIV care and prevention among men, on post-partum ART continuation and adherence among HIV-positive women. We will recruit HIV-positive women in PMTCT B+ programs in Kampala to be randomized to: 1) the intervention arm in which they receive HIVST kits for their partners with self-instruction materials about HIVST, encouragement to seek confirmatory testing and counseling along with a voucher and referral, and brief educational materials about PrEP and ART, or 2) the control arm in which they receive invitation letters to deliver to their partners that invite men to fast-track HIV testing at the clinic, along with brief educational materials about PrEP and ART. Women in the intervention arm will be instructed in the use and interpretation of HIVST and be provided two HIVST kits to give to or use with their male partners. Male partners will receive an educational brochure outlining the benefits of HIV testing and ART or PrEP. We will receive an educational brochure outlining the benefits of HIV testing and ART or PrEP. We will recommend that HIV-negative men use PrEP until their partner has achieved viral suppression, and that HIV-positive men take ART.

The co-primary outcomes of the study are the proportion of male partners who test and the proportion of HIV-negative male partners who take PrEP. The primary analysis is an intent to treat comparison by randomization arm of the primary outcome: proportion of women whose male partners who test HIV-uninfected and initiate PrEP within six months after their HIV-positive partner is randomized. A secondary outcome is an objective marker of PrEP adherence - tenofovir detection at 3 and 6 months - among men who initiate PrEP.

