#### PrEP adherence

High adherence is important for PrEP effectiveness in preventing HIV acquisition. Study staff also will provide brief adherence counseling at each scheduled visit, to mimic "real world" counseling. Data on adherence to the product use regimen will be collected via standardized intervieweradministered questions to ascertain product use. PrEP use will be measured by dispensing records, and self-report through a validated 3-item questionnaire. Clinic and pharmacy records will be used to document PrEP prescriptions at the ANC clinics and IDI Kasangati, abstracted in real time from pharmacy records and entered into an electronic database. Adherence will also be assessed through tenofovir drug levels in male partners 3 and 6 months after PrEP initiation.

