#### Retention

Retention measures for pregnant women and male partners will be those regularly used in previous PrEP studies at the IDI Kasangati – reminder calls, text messages, peer support, and home visits when individuals have several missed visits or an abnormal test result. Couples who break up will remain in the study but have separate clinic visits. We will continue to collect data about sexual behavior and PrEP and ART use. Research procedures for men will include behavioral questionnaires and blood collection to test for tenofovir drug concentration levels among men using PrEP.

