#### Outcome measurements

Aim 1: Women who are randomized will have key outcomes assessed at scheduled visits. The co-primary outcomes will be HIV testing by the male partner, as measured by questionnaires administered to women in clinic, and PrEP by 6 months after the woman initiated ART. The Kenya pilot indicated minimal bias in self-report of male partner testing. The secondary outcome is PrEP adherence among the male partners who initiate PrEP, based on detectable blood tenofovir levels at 3 and 6 months after PrEP initiation. PrEP use will also be measured by pharmacy records where men are dispensed PrEP (e.g.at the ANC or IDI Kasangati), and self-report through a validated 3-item questionnaire[83]. We will assess HIV seroconversion but expect a low rate.

Aim 2: The exposures of interest are male partner testing, PrEP initiation and ART initiation (Table 2). The primary outcome is the woman's viral load at 12 months post-partum. Viral suppression will be defined as plasma viral load <400 copies/ml). For the secondary outcomes, pharmacy records will be used to measure ART dispensation and women will be asked at quarterly visits about treatment interruptions[83]. Secondary outcomes include infant HIV status at 6 weeks (HIV-infected/uninfected) which will be ascertained from ANC records, and infant survival at 12 months as reported by the mother at her 12-month post-partum visit.

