#### Statistical considerations

Aim 1: The primary analysis will be an intent to treat comparison by randomization arm of the primary outcome: the proportion of women whose male partners who test for HIV and the proportion of HIV-negative men who take PrEP within six months after their HIV-positive partner is randomized. The secondary outcome is tenofovir detection at 3 and 6 months among men who use PrEP.

Aim 2: Our primary analysis will assess the effect of male partner's PrEP or ART use on women's ART continuation and viral suppression at 12-month post-partum period, as the measure of her ART continuation and adherence. This intent of the analysis is to assess the impact of the male partner's current (time-dependent) PrEP or ART use on the women's current ART use and viral suppression. Since initiation of PrEP or ART is secondary to the randomized HIV testing intervention, causal inference methods will be used to assess the impact of male partner HIV testing and PrEP or ART use on post-partum ART continuation. We will calculate standardizedinverse-probability weights with logistic regression [84], to predict the probability of current male PrEP or ART use at each visit as predicted by the instrumental variable HIV testing randomization, and potential time-varying confounders (Table 3), including sexual behavior, future fertility desires, relationship power dynamics, intimate partner violence, alcohol use, and baseline demographics and duration of ART pre-partum. These weights will then be used in a pooled logistic regression model of partners' PrEP or ART exposure as predictors of: 1) ART continuation and 2) viral suppression. In a separate set of models, we will examine the direct effect of male testing, overall and separately for HIV-positive and HIV-negative men, on the woman's ART continuation and viral suppression. We will also explore an instrumental variables approach to causal estimation, given the expected role of randomization in male partners' initiation of PrEP and ART in Aim 1[85].

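### Tenofovir adherence is defined at 3 and 6 months after PrEP initiation among initiators, but Protocol Table 6 draws blood by time since enrolment and only from men on PrEP

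*Protocol*

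**What the plan says.** **Time origin.** Protocol, Outcome measurements (Aim 1) bases the outcome on levels "based on detectable blood tenofovir levels at 3 and 6 months after PrEP initiation". Protocol, PrEP adherence agrees: "Adherence will also be assessed through tenofovir drug levels in male partners 3 and 6 months after PrEP initiation".

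**Population.** Outcome measurements describes the outcome as "PrEP adherence among the male partners who initiate PrEP", and Overall design as "tenofovir detection at 3 and 6 months - among men who initiate PrEP". Statistical considerations (Aim 1) differs: "The secondary outcome is tenofovir detection at 3 and 6 months among men who use PrEP". The Aim 1 text under Objectives also refers to users and, like Statistical considerations, gives no time origin. Retention describes "blood collection to test for tenofovir drug concentration levels among men using PrEP".

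**Schedule.** In Protocol Table 6 the row "Blood sample archive for tenofovir levels (if on PrEP" is marked at M3 and M6 and blank at M9, M12 and [M]. The M3 footnote reads "Three months after study enrollment". SAP 3.4.1 also counts male visits quarterly from enrolment.

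**When PrEP can start.** Table 6 marks PrEP provision at enrolment, M3 and M6, and in brackets (as indicated) at M9, M12 and [M]. SAP 7.3.3 counts PrEP initiation up to the end of the study.

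**SAP.** Tenofovir is not among the secondary endpoints in SAP 2.2.2, and the missing-data rules in SAP 5.3 do not mention it.

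**The concern.** The outcome definition and the collection schedule use different clocks and different populations. A site that follows Table 6 exactly will not collect the outcome described under Outcome measurements, except for men who start PrEP at enrolment and remain on it.

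This is the only objective marker of PrEP adherence in the trial. If men who have stopped leave the denominator, the figure answers a narrower question (whether men still on PrEP have drug in their blood) while carrying the label of adherence among initiators. A reader would take it as more favourable than it may be.

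**Working it through.** The documents state no sample size, power or expected rate for this outcome, so there is no figure of the plan's own to reproduce. The check maps the schedule onto the definition and then illustrates the denominator effect.

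**1. Draw times by start visit.** Months since initiation = draw visit (3 or 6) minus start visit. Only positive values are on-drug draws.

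| PrEP start | Draw at M3 | Draw at M6 | Against the definition |
|---|---|---|---|
| Enrolment | 3 | 6 | both obtained |
| One month after enrolment | 2 | 5 | both early |
| M3 | none | 3 | 6-month draw missing |
| M6, M9 or M12 | none | none | both missing |

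Applying the enrolment clock to M6 as well as M3 is a reading of the column sequence. SAP 3.4.1 supports it.

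**2. Men who stop.** A man off PrEP at M3 or M6 fails the Table 6 condition, so no blood is archived. No section scores him as undetected, and the *use* wording under Objectives, Retention and Statistical considerations leaves him out. The exception is a seroconverter, for whom Table 7 has a separate archive for PrEP levels.

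**3. Illustration of the denominator.** Let D be detection among men on PrEP and s the share of initiators who have stopped by the draw, with no detection in those who stopped. Detection among all initiators = D × (1 − s). Take D = 0.82, borrowed from the earlier demonstration project in the Protocol background; s is assumed.

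| s | D × (1 − s) | Figure from men on PrEP | Gap (points) |
|---|---|---|---|
| 10% | 0.82 × 0.90 = 0.738 | 82% | 8.2 |
| 20% | 0.82 × 0.80 = 0.656 | 82% | 16.4 |
| 30% | 0.82 × 0.70 = 0.574 | 82% | 24.6 |
| 40% | 0.82 × 0.60 = 0.492 | 82% | 32.8 |

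**4. Scale.** Protocol Table 3 gives 500 women, 2:1 allocation, 95% retention, 80% PrEP uptake, 60% or 70% HIV-negative men, and test uptake of 20% or 30% (control) and 55% or 65% (intervention).

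- Lowest: 500 × 0.95 × (0.20/3 + 0.55 × 2/3) × 0.60 × 0.80 = 98.8 initiators.
- Highest: 500 × 0.95 × (0.30/3 + 0.65 × 2/3) × 0.70 × 0.80 = 141.9 initiators.

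With about 99 to 142 initiators, each man who is neither sampled nor counted is 0.7 to 1.0 percentage point of the intended denominator (1/142 to 1/99).

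**The case against.** **The clocks coincide on the usual pathway.** A man enrols by coming for testing and can be offered PrEP at that visit. If he starts then, Table 6 samples him correctly. The documents give no share of late starters. Provision at M9, M12 and [M] is only as indicated, and PrEP is tied to roughly the first six months of the woman's ART, so first starts at M6 or later may be few. This stands as a limit on size. It does not remove the mismatch: the schedule allows later starts and has no draw for them.

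**Detection among current users is a legitimate measure.** It describes adherence while on drug, and stopping is visible in dispensing records and self-report. This stands too, and it is why both figures should be reported. But the protocol also names initiators as the population, and the two cannot share one label.

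**PrEP is time-limited.** Some men off PrEP at M6 will have stopped as planned, and counting them all as non-adherent would be wrong. This stands and is carried into the fix.

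**The percentages are assumptions.** The 82% is a share of plasma samples, not stated to come only from people still on drug, and no stopping rate is given. The table in step 3 shows how the effect works and is not an estimate.

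**Stronger readings the documents do not support.**
- A reader might infer that a man starting at M3 has a pre-dose sample that is misread as non-detection. The same on-PrEP condition rules that draw out.
- A reader might infer bias in a comparison between arms. No arm comparison of tenofovir is planned.
- A reader might infer that early stopping is the main form of non-adherence. Nothing in the documents says so.

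**Conclusion.** The inconsistency is real and can be read directly from the protocol. The outcome is set on an initiation clock among initiators, while Table 6 collects it on an enrolment clock among men on PrEP. Late starters lose one or both draws. Initiators who have stopped have neither a sample nor a counting rule. The SAP does not repair this; because it covers only selected secondary objectives, the missing endpoint is not counted here as a separate error.

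The reported figure can overstate adherence among initiators by an unknown amount. The illustrative range of 74% down to 49%, against 82%, rests on an assumed 10% to 40% stopping, no drug detected in men who stopped, and 82% applying to men on PrEP. If part of the stopping is planned, the gap that reflects poor adherence is smaller.

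This should be corrected, but it concerns a secondary outcome. The co-primary analyses of partner testing and PrEP initiation do not depend on it.

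**What to change.** 1. **Timing.** In Table 6, tie the tenofovir archive to the quarterly visits nearest 3 and 6 months after each man's first PrEP dispensation, allowing M9, M12 or [M] for later starters. This is still at most two draws per man.
2. **Denominator.** Use one population, men who initiated PrEP, in Overall design, Objectives (Aim 1), Retention, Outcome measurements, Statistical considerations and Table 6.
3. **Reporting.** At each time point give:
   - (a) the number of initiators, the number still on PrEP by dispensing records (with any of these lacking a sample), the number who stopped, and the number whose follow-up ended before the time point;
   - (b) detection among men sampled while on PrEP;
   - (c) among all initiators who reached the time point, the proportion on PrEP with tenofovir detected, with planned and unplanned stopping shown separately.
4. **Reconcile first.** The statements on how long PrEP is recommended differ. Protocol, Overall design refers to the partner's viral suppression. Protocol, PrEP medication and dispensation refers to six months or suppression. The SAP protocol summary refers to at least six months of ART and suppression. These must be reconciled before stopping can be classed as planned or unplanned.

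**Cost.** The change is to table and outcome wording, using existing quarterly visits and dispensing records already collected. The downside is a few more archived tubes at later visits and possibly a lower reported figure.
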